11.2 Sample Size /Justification

We expect to see higher grades of WHO COVID ordinal clinical scale in control group compared to the CSA treatment group, and propose to use a 1 to 2 randomization in favor of CSA group.

The total sample size of 75 evaluable participants will provide 81% power to reject the null hypothesis that the grade in control group is less than or equal to the CSA group with a 10% one-sided significance level when the true effect size, as measured by the probability that

Control grade is greater than CSA grade, is 0.65 or greater. Sample size and/or power for the various scenarios were calculated using nQuery 8 (StatSols Version 8.5.2.0).

The following provides the rationale for the alternate hypothesis effect size. We have assumed that all participants will be starting in category 4. Based on review of hospital data, about one third of such patients end-up in the ICU and about half of those patients will die. Of the two thirds that do not go to the ICU, most will be discharged in 2 weeks or less. We have therefore hypothesized that at 2 weeks following enrollment, the control group will be distributed as shown in the table 3.

We have hypothesized several scenarios to estimate the sample size needed to detect a CSA effect with reasonable power. We expect the effect of CSA will be to reduce ICU admissions, or to shorten time in the ICU and reduce deaths, so that the fraction in categories 6, 7, and 8 on Day 14 will be reduced and less ill patients will go home earlier, increasing the fraction of 1 and 2's on day 14.

Since the outcome is ordinal, a Wilcoxon rank sum test is used to control (no CSA) and CSA on day 14. The one-tailed null hypothesis is that the distribution of WHO scores is the same in two groups or worse in CSA, and the alternative is that the distribution of WHO scores in the CSA group is shifted lower. The effect size ($P_1 = \Pr(\text{Control} > \text{CSA})$) is the probability that a randomly selected observation from the control group has a score greater than one from CSA group. The null value for P_1 is 0.5 and the closer P_1 to 1, the bigger the effect.

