A sample size of 25 in the control group and 50 in the CSA group will have 81% power to reject the null hypothesis (based on the 8 observable category probabilities for each group shown in table 3) in favor of the alternative hypothesis that an observation in the control group has a higher score on day 14 than an observation in the CSA group using a Wilcoxon (Mann-Whitney) rank-sum test with the type 1 error of 10% one-sided significance level.

Table 3. Scenarios and associated sample size and power.

		At Accrual	Control	CSA Scenario 1 ~50% benefit	CSA Scenario 2 ~40% benefit	CSA Scenario 3 ~30% benefit
8	Death	0	17%	8%	10%	12%
7	Hospitalized, vented, pressors	0	8%	4%	5%	5%
6	Hospitalized w invasive ventilation	0	8%	4%	5%	6%
5	Hospitalized non-invasive ventilation	0	5%	2%	3%	3%
4	Hospitalized on O2	100%	5%	2%	3%	3%
3	Hospitalized not on O2	0	10%	2%	4%	7%
2	Not hospitalized with symptoms	0	24%	39%	35%	32%
1	Not hospitalized with no symptoms	0	23%	39%	35%	32%
Effect Size (P1=Pr(Control>CSA)				0.65	0.61	0.59
Power & sample size ($\alpha=10\%$, 1-tailed)						
	Power with N=25 control, 50 CSA			81%	62%	48%
	Sample size for ~80% power; Ctl:CSA			25:50	45:90	75:150

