11.5 Analysis of Secondary Endpoints

The secondary objectives are mostly concerned with the safety and effects of Neoral (CSA) in this patient population. The secondary endpoints include Neoral-associated toxicity events, serum inflammatory markers (CRP, d-dimer, ferritin, ANC, absolute lymphocyte count, WBC, PLT (daily while inpatient and including day 14 and 28 for those discharged), Viral load (days 14 and 28), vital status (days 14 and 28), disease improvement (days 14 and 28), proportion of those requiring invasive mechanical ventilation, incidence of deep vein thrombosis, proportion of patients discharged on day 28, time to hospital discharge, and disease resolution (days 14 and 28).

For safety, Neoral-associated toxicity events include nephrotoxicity, resistant hypertension, hepatotoxicity, signs of CNS toxicity, or superinfection. AE's and SAE's by CTCAE v5 will be summarized descriptively with frequencies and rates. Rates and 95% CI's of grade 3 and above AE's will be reported.

Serum inflammatory markers are viewed as interval scales and after appropriate normalizing transformation (if needed), will be analyzed using general linear mixed models to account for within patient dependencies to allow comparisons between groups.

Viral positivity between groups at days 14 and days 28 will be tested by Wilcoxon rank sum test.

Survival analysis methods will be used to describe overall survival experience, to estimate survival at selected time points, and to compare groups. Cumulative incidence analysis methods will be used if there are competing risks. The same approach will be used with disease improvement (alive and free invasive or non-invasive mechanical ventilation) and disease resolution (alive and discharged home without oxygen).

Fisher's exact test will be used to compare rates of need for invasive mechanical ventilation bench marked to a particular time, and ever need. If required, this endpoint will include deaths before intubation in the rare cases in which this occurs.

In exploratory analyses, we will use logistic regression to model ventilator need as a function of treatment group and other baseline characteristics. Survival analysis methods will be used to analyze time to mechanical ventilation, with censoring at last follow-up for those not needing ventilation.

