Day 28 discharge will be trichotomized as death prior to day 28, discharge by day 28, hospitalized after day 28. Groups will be compared using Chi square test for independence.

Survival analysis methods will be used with death prior to discharge considered as a competing risk.

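### Fisher's exact test for need for invasive ventilation is valid but conservative at 25:50, and no level or sidedness is set for it; Boschloo's test would recover some power at almost no cost

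*Combined protocol and SAP*

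**What the plan says.** Section 11.5 states that Fisher's "exact test will be used to compare rates of need for invasive mechanical ventilation", once at a benchmark time and once for any need at all. Two 2×2 comparisons are therefore planned. The section allows deaths before intubation to be counted if required. It gives no level, sidedness, power or reason for choosing Fisher.

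The only level set for an efficacy comparison is in section 11.2, for the primary Wilcoxon test: a "rank-sum test with the type 1 error of 10% one-sided significance level". The same section fixes the arms: "A sample size of 25 in the control group and 50 in the CSA group will have 81% power to reject the null hypothesis". Table 3 gives day-14 score distributions for control and three cyclosporine scenarios. No ventilation rate as such appears anywhere.

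Elsewhere in section 11.5, PCR positivity is compared by the Wilcoxon test. For three-category day-28 status, "Groups will be compared using Chi square test for independence".

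**The concern.** Fisher's test conditions on both margins of the table. In a randomised two-arm trial only the arm sizes are fixed; the number of events is not. With 25 and 50 patients the conditional distribution is coarse, so the attainable level usually falls well short of the nominal one. An unconditional exact test keeps the nominal level as an upper bound and uses more of it.

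Need for invasive ventilation is objective 1.2.6, and section 11.2 expects cyclosporine to reduce the share of patients in scores 6, 7 and 8, so the endpoint lies close to the hypothesised benefit. The Wilcoxon and chi-square choices elsewhere in section 11.5 show that conditional exact testing is not a general policy of the plan. At stake is some power on one secondary comparison in a 75-patient trial. Separately, its result cannot be read against a prespecified criterion, because none is stated.

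**Working it through.** **1. The plan's own figure.** Table 3, Scenario 1, from score 8 down to 1: control 17, 8, 8, 5, 5, 10, 24, 23%; cyclosporine 8, 4, 4, 2, 2, 2, 39, 39%. The effect size is Pr(Control > CSA) plus half the ties:

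0.17×0.96 + 0.08×0.90 + 0.08×0.86 + 0.05×0.83 + 0.05×0.81 + 0.10×0.79 + 0.24×0.585 + 0.23×0.195 = 0.650, matching the stated 0.65.

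Noether's formula, with control share c = 1/3 and N = 75: z = √[12·c(1−c)·N·(0.15)²] − 1.2816 = √(200×0.0225) − 1.2816 = 0.840, so power is 80.0%. Simulation of the Wilcoxon test (100,000 runs) gives 82.9% with tie correction and 81.3% without. The stated 81% is reproduced, so the Table 3 inputs are being read as intended.

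**2. Inputs for the ventilation comparison.** Arms are 25 and 50 (section 11.2). The event rate is assumed to be the sum of scores 6, 7 and 8 on day 14:
- control 8 + 8 + 17 = 33%
- Scenario 1: 4 + 4 + 8 = 16%
- Scenario 2: 5 + 5 + 10 = 20%
- Scenario 3: 6 + 5 + 12 = 23%

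**3. Method.** All 26 × 51 = 1,326 possible tables are enumerated. With x control and y cyclosporine events, the one-sided Fisher p-value is Pr(X ≥ x), where X is hypergeometric given x + y events among 75. Fisher rejects if p ≤ α. Boschloo rejects if p ≤ c, where c is the largest cut-off whose rejection probability, maximised over the common event rate, stays at or below α. Power is the sum of Bin(x; 25, p₁)·Bin(y; 50, p₂) over the rejection region.

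**4. One-sided 10% (the primary test's level, carried over as an assumption).** Fisher's maximum true level over all common rates is 6.6%, and it lies between 5.5% and 6.5% for rates of 15 to 35%. For Boschloo, c = 0.1407 with maximum level 9.99%; the next attainable cut-off, 0.1415, gives 10.001% and is excluded. Because c exceeds 0.10, Boschloo rejects every table that Fisher rejects, plus 25 more. One such table is 7/25 against 7/50: Fisher p = 0.126, Boschloo p = 0.084.

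| Rates | Fisher | Boschloo | Gain (points) |
|---|---|---|---|
| 33% vs 16% | 54.7% | 60.7% | 5.9 |
| 33% vs 20% | 38.3% | 44.2% | 5.9 |
| 33% vs 23% | 27.6% | 33.2% | 5.7 |

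Gains are taken from unrounded values. If deaths are left out (scores 6 and 7 only: 16% against 8, 10 or 11%), the gains are 7.1, 6.4 and 5.8 points.

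**5. Other levels.** At two-sided 5% with the usual minimum-likelihood Fisher p-value, the maximum level is 4.1% for Fisher and 4.5% for Boschloo. Power goes from 32.5, 18.5 and 11.5% to 35.3, 21.4 and 13.8%, a gain of 2 to 3 points. For 33% against 16%, the choice of level and convention matters as follows:

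| Level | Fisher | Boschloo | Gain (points) |
|---|---|---|---|
| One-sided 5% | 38.3% | 49.2% | 10.9 |
| One-sided 2.5% | 29.3% | 37.7% | 8.3 |
| Two-sided 10% | 46.1% | 52.0% | 5.9 |
| Two-sided 5%, doubled p | 29.3% | 37.7% | 8.3 |
| Two-sided 5%, usual p | 32.5% | 35.3% | 2.8 |

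**6. Other splits.** Moving one patient between arms (24:51 or 26:49) gives gains of 7 to 11 points at one-sided 10%. At two-sided 5% the gain is about 5 to 7 points at 24:51 and below 2 points at 26:49. It was never negative.

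**The case against.** The strongest reply is that Fisher's test is valid, prespecified and customary in small samples, and that conditional against unconditional inference is an old argument in which neither side is in error. That stands as far as it goes: the planned test protects the type I error. It does not show any loss from switching, since the event total is not fixed by this design and Boschloo's rejection region contains Fisher's.

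Second, one-sided 10% is stated only for the primary test. This stands, and it makes the 6-point figure conditional. At two-sided 5% the shortfall in maximum level is small (4.1% against 4.5%). Up to eight strata and possible dropout also make an exact 25:50 split uncertain, so no single gain should be quoted without its conditions.

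Third, a reader might infer that ventilation alone is penalised among the categorical endpoints, or that the trial discards its information on ventilation. The documents support neither reading. Deep vein thrombosis incidence is also binary and has no named test. Day-28 status has three categories, so its chi-square test is not a like-for-like contrast. Section 11.5 also analyses ventilation by exploratory logistic regression and by time-to-event methods, and the primary ordinal test already uses scores 6 to 8. Nor does section 11.2 single out ventilation: it also expects fewer deaths, shorter ICU stays and earlier discharge, and 17 of the 33 control percentage points in the proxy are deaths.

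Finally, this is one of about ten secondary objectives, with no decision rule attached. That stands too, and limits the importance of the point.

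**Conclusion.** The point holds as a modest gain in efficiency. At 25:50 Fisher's test is conservative for both planned ventilation comparisons, and the plan leaves their level and sidedness open. At one-sided 10%, Boschloo's test adds about 6 points of power in each Table 3 scenario; at two-sided 5% with the usual p-value it adds about 2 to 3. The direction was the same under every level, convention and split examined; the size was not.

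The figures rest on three assumptions: the level is borrowed from the primary test or set by convention; day-14 scores 6 to 8 stand in for need for ventilation, although the rate of ever needing it could be higher; and the arms are 25 and 50 with no loss. A reader might infer that the planned test is wrong or that changing it would make the comparison adequately powered. Neither follows: Fisher controls the type I error, and power at one-sided 10% reaches only about 61% at best at 25:50 on the scores 6 to 8 rates. The primary analysis is untouched.

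**What to change.** In section 11.5, before any outcome data are seen:
- name Boschloo's exact unconditional test for both ventilation comparisons, at the benchmark time and for ever needing ventilation;
- state the level and sidedness, and for a two-sided test the p-value convention used;
- report the risk difference with a confidence interval, naming its method and level;
- keep Fisher's exact test as a sensitivity analysis.

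The level and sidedness should be stated even if Fisher remains the main test.

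The cost is a few lines of SAP text and one function call in standard software. No patients, data or procedures change. The downside is a less familiar test name.

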1.2 Secondary Objectives

- 1.2.1 To establish the safety of Neoral in this patient population (adverse events).
- 1.2.2 To determine the effect of Neoral on serum inflammatory markers (CRP, d-dimer, ferritin, ANC, absolute lymphocyte count, WBC, PLT (daily while inpatient and including day 14 and 28 for those discharged).
- 1.2.3 To determine the effect Neoral on viral SARS-CoV2 PCR positivity from baseline (day 0 to -2) before receiving Neoral) to day 14, and from baseline to day 28.
- 1.2.4 To determine the effect of Neoral on survival (days 14 and 28)
- 1.2.5 To determine the effect of Neoral on disease improvement (alive and free of invasive or non-invasive mechanical ventilation; days 14 and 28).
- 1.2.6 To determine the effect of Neoral on proportion of those requiring invasive mechanical ventilation.
- 1.2.7 To determine the effect of Neoral on incidence of deep vein thrombosis.
- 1.2.8 To determine the effect of Neoral on proportion of patients discharged on day 28.
- 1.2.9 To determine the effect of Neoral on time to hospital discharge.
- 1.2.10 To determine the effect of Neoral on disease resolution (alive and discharged home without oxygen; days 14 and 28).

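### The ventilation analyses in Section 11.5 have no fixed, consistent rule for patients who die without being ventilated

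*Combined protocol and SAP*

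**What the plan says.** Objective 1.2.6 is "To determine the effect of Neoral on proportion of those requiring invasive mechanical ventilation". Section 11.5 of the combined protocol and SAP serves it with three analyses.

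- **Rate (secondary).** Fisher's "exact test will be used to compare rates of need for invasive mechanical ventilation bench marked to a particular time, and ever need". The particular time is not given. On deaths, the plan says: "If required, this endpoint will include deaths before intubation in the rare cases in which this occurs". It does not say what would make inclusion required, who decides, or when.
- **Logistic model (exploratory).** "In exploratory analyses, we will use logistic regression to model ventilator need as a function of treatment group" and other baseline characteristics. Death is not mentioned.
- **Time to mechanical ventilation (exploratory).** Survival methods, "with censoring at last follow-up for those not needing ventilation". Death is neither an event nor a competing risk.

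Elsewhere the same section does deal with death. In the overall-survival paragraph: "Cumulative incidence analysis methods will be used if there are competing risks". It continues, "The same approach will be used with disease improvement", and adds disease resolution. For discharge: "Survival analysis methods will be used with death prior to discharge considered as a competing risk". Ventilation is not on either list.

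**The concern.** Death without intubation prevents intubation from ever being observed. A ventilation endpoint therefore needs a stated rule for such patients, and one rule should serve all the ventilation analyses. Here the secondary rate has an optional rule, the time-to-event analysis has an implicit one (censor at death) and the logistic model has none.

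The optional rule matters most, because it belongs to a secondary endpoint. If deaths are left out of the Fisher rate, a patient who dies unventilated sits in the no-ventilation column beside patients who recovered. The trial is open-label (Sections 4.3 and 11), and Section 11.6.3 exempts the study statistician from the restriction on summary outcome data. The choice could thus be made by someone who knows which way it moves the result. Censoring at death treats the patient as still able to be ventilated later, which is hard to defend if the curve is read as the risk of ventilation.

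**Working it through.** The plan states no rate, power or sample size for any ventilation endpoint, so there is no figure to reproduce. The check has two parts.

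**1. Following one patient through the text.** Take a patient who dies on the ward without intubation. Section 6.4 ends follow-up at death, so last follow-up is the death date.

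| Analysis (Section 11.5) | How this patient counts |
|---|---|
| Fisher rate, deaths added | Event |
| Fisher rate, deaths not added | No ventilation |
| Logistic model | Not stated; a non-event if need means ventilation alone |
| Time to ventilation | Censored at death |
| Time to discharge | Competing event |

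**2. Size, using Table 3.** Inputs for day 14:

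- Control: death 17%, score 7 8%, score 6 8%.
- CSA scenario 1: death 8%, score 7 4%, score 6 4%.
- Arm sizes: 25 control, 50 CSA.
- Assumption: f, the share of day-14 deaths never intubated, varied from 0 to 1 because the documents do not give it. Patients extubated alive before day 14 are ignored.

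Ventilated = scores 6 + 7 + deaths × (1 − f).

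Ventilated or dead = scores 6 + 7 + deaths, whatever f is: control 8 + 8 + 17 = 33%; CSA 4 + 4 + 8 = 16%; difference 17 points.

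| f | Control, ventilation alone | CSA, ventilation alone | Difference (points) | Expected unventilated deaths, control / CSA |
|---|---|---|---|---|
| 0 | 33% | 16% | 17 | 0 / 0 |
| 0.1 | 16 + 17×0.9 = 31.3% | 8 + 8×0.9 = 15.2% | 16.1 | 0.4 / 0.4 |
| 0.25 | 16 + 17×0.75 = 28.75% | 8 + 8×0.75 = 14.0% | 14.75 | 1.1 / 1.0 |
| 0.5 | 16 + 17×0.5 = 24.5% | 8 + 8×0.5 = 12.0% | 12.5 | 2.1 / 2.0 |
| 1 | 16% | 8% | 8 | 4.25 / 4.0 |

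In scenarios 2 and 3 ventilated-or-dead is 33% against 20% and 23%. Ventilation alone at f = 0.5 is 24.5% against 15.0% and 17.0%.

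**Unequal f (constructed example).** Let ventilation or death be the same in both arms: 8/25 and 16/50, 32% each. Suppose 0 control and 6 CSA patients die unventilated. Ventilation alone is then 8/25 = 32% against (16 − 6)/50 = 10/50 = 20%, a 12-point difference with no difference in the composite. Fisher's two-sided p is 0.27, so it would not be a significant finding, but the estimate misleads.

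**Time to ventilation.** Let v be the proportion ventilated and d the proportion dying unventilated, with constant cause-specific hazards. Censoring at death gives 1 − KM = 1 − exp[ln(1 − v − d) × v/(v + d)], against a cumulative incidence of v.

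- Control, f = 0.5 (v = 0.245, d = 0.085): 25.7% against 24.5%.
- Control, f = 1 (v = 0.16, d = 0.17): 17.6% against 16.0%.
- CSA scenario 1, same two values of f: 12.3% against 12.0%, and 8.3% against 8.0%.

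The inflation is therefore 1.2 to 1.6 points in control and about 0.3 in CSA at these values of f, and less when f is lower.

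**The case against.** The best defence of the rate is that its opening condition simply means that deaths will be added if any occur. On that reading the plan already uses ventilation or death. The reading is natural, but the text does not settle it. The sentence also calls such deaths rare, without a figure. If f is near 0.1, the table shows under one patient per arm and a shift of about one point.

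Second, censoring at death is a standard way to estimate a cause-specific hazard. It misleads only if the result is read as incidence, and the plan does not name its estimator. That is fair, and the distortion is small in any case.

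Third, the general competing-risk sentence might be meant for all of Section 11.5. But the next sentence names the endpoints it extends to, and the ventilation text then sets its own censoring rule.

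Fourth, other endpoints protect the trial. Death is score 8 on the primary scale, vital status is analysed separately, and objective 1.2.5 counts a death as failure. This stands, and it limits the consequences.

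A reader might go further and infer that every ventilation analysis scores death as avoiding ventilation, so that replacing intubation with unventilated death would look beneficial in all three. The documents do not support that. Censoring removes the patient from the risk set, and 1 − KM slightly overstates ventilation. The Fisher rate is free of the problem if deaths are added, as the plan allows. The logistic model leaves the matter unstated.

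**Conclusion.** The concern holds as a gap in definition and an inconsistency. The part that matters is the optional handling of deaths in the secondary Fisher comparison; the time-to-ventilation and logistic analyses are exploratory. The effect on the rate is anywhere from nothing (f = 0) to a fall in the apparent difference from 17 to 8 points (f = 1) under Table 3 scenario 1. This rests on an assumed f and ignores patients extubated alive before day 14. It would be wrong to infer a bias that always favours CSA: with the same f in both arms, leaving deaths out shrinks the benefit, and a false benefit needs an imbalance in unventilated deaths between arms. The primary conclusion is not at risk. The change is worth making before outcome data are examined, because the rule should not depend on what the data show.

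**What to change.** In Section 11.5:

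- Delete the opening condition from the sentence on deaths. Define the Fisher endpoint as invasive ventilation or death without it, by a stated day within the 60-day follow-up.
- For time to ventilation, use cumulative incidence with death without ventilation as a competing event, or analyse the composite. Keep patients discharged alive in the risk set to the stated day.
- Use the same definition in the logistic model.
- Report ventilation alone and unventilated deaths separately by arm.

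The cost is a wording change. The WHO score is already scheduled through hospital stay and at days 14, 28 and 60 (Table 1), and follow-up covers death. The downside is that the composite somewhat broadens objective 1.2.6 and overlaps with objective 1.2.5. The wording of 1.2.6 should be aligned with it, and showing the components separately keeps the ventilation question visible.
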